5 STUDY ENROLLMENT AND WITHDRAWAL

Practitioner: Practitioners may withdraw from the study before randomization and be replaced. After randomization, they will not be replaced.

For this study, the term "practitioner" will be limited to dentists only who are licensed in the US to treat patients on a recurring basis. Hygienists will not be included in this study due to the pre-and post-study vignettes which include clinical scenarios and operative decisions.

Patient: Patients under the age of 19 (this age may vary by state) will need to have the informed consent signed by the parent or legal guardian, as well as provide assent. Racial and ethnic minorities will be included in the study at least proportional to their composition in the dental community. Emancipated minors will be treated as adults, as allowed by regional IRBs.

5.1 Subject Inclusion Criteria

Practitioner: In order to be eligible to participate in this study, an individual must meet all of the following criteria:

- Is enrolled in the National Dental PBRN;
- Has completed an Enrollment Questionnaire;
- Is a general or pediatric dentist who is licensed in the United States to treat patients and treats patients in the United States on a recurring basis;
- Is trained and certified in Human Subjects Protection Training;
- Has attended or viewed a National Dental PBRN orientation session or attended at least one annual regional meeting of practitioners or has attended a National Dental PBRN workshop at IADR or AADR.
- Performs restorative dentistry routinely in their practices as reported on the enrollment questionnaire;
- Has no clinical experience (no history of routine use in practice within the past one year) with either of the devices being used in the study and declares no conflict of interest with the corporations that produce DIAGNOdent[®] and Spectra[®]; and
- Is able to complete the pre-and post-study vignettes online.

Practice: If a practitioner is in a practice where they share an operatory (including a hygiene chair) only 1 dentist can be recruited from that practice.

Patient: In order to be eligible to participate in this study, an individual with a SOCL must meet all of the following criteria:

- Willing to provide consent according to regionally approved procedures and/or obtain parent/legal guardian permission as applicable;
- Willing to comply with all study procedures;

- Is six years of age or older; and
- Has not participated in the study previously. (Patients will be enrolled only once throughout the study (this includes the pre-intervention and intervention phases for the pilot study and full study).

Tooth: In order to be eligible to be included in this study, a tooth with a SOCL must meet all of the following criteria:

- Permanent tooth;
- No radiographic evidence of caries into dentin based on available radiographs;
- Caries into dentin is suspected due to roughness, surface opacities, or staining;
- No symptoms of sensitivity to sweets, cold, air, etc.;
- No restoration on the occlusal surface; and
- No sealant on occlusal surface.

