11 STATISTICAL CONSIDERATIONS

11.1 Study Hypotheses

The primary objective of the study is to quantify the difference in proportions of SOCL that are treated operatively among the study groups. The null hypothesis for this objective is that the proportions of SOCL that are treated operatively are not different among the three study groups. The corresponding alternative hypothesis is that the proportion of SOCL treated operatively differs among the groups. The main interest is in comparing the proportions of SOCL treated operatively between each of the device groups and the no-device group. The null hypothesis that will be tested for each of these comparisons is that the proportions of SOCL treated operatively does not differ between the groups versus the alternative hypothesis that the proportions differ. The study will also quantify the differences in proportions of SOCL that extend into dentin, among those that are treated operatively in each study group. The null hypothesis is that there is no difference among the groups in the proportion of operatively treated SOCL that extend into dentin. The alternative hypothesis is that the proportions of operatively treated SOCL that extend into dentin differ among the groups. Here again, there is particular interest in the two pre-planned comparisons between each of the device groups and the no-device group. The null hypothesis for each of these comparisons is that there is no difference in the proportions of SOCLs that extend into dentin between the device and no-device groups, and the alternative hypothesis is that there is a difference in the proportions.

A secondary objective of the study is to identify clinical characteristics of operatively-treated SOCLs that predict caries extending into dentin. For each of the clinical characteristics that is considered, the null hypothesis is that there is no association with extension into dentin and the alternative hypothesis is that there is an association with extension into dentin. Practically, the goal will be to identify a multivariable statistical model that is predictive of caries extending into dentin. In addition to separate tests for each characteristic, the null hypothesis for the predictive model is that the set of clinical characteristics included in the model jointly have no association with caries extension into dentin. The alternative hypothesis is that a joint association is present.

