The analysis data set for identification of clinical characteristics of SOCLs that predict caries extending into the dentin will include all SOCLs that were treated operatively by the study practitioners. The outcome variable will be a dichotomous variable indicating whether the lesion extended into the dentin. The primary statistical model will be mixed-model logistic regression, implemented with GEE in order to account for clustered observations. Clinical characteristics that will be evaluated as potential predictors of caries extending into dentin are luster, color, roughness on examination with explorer, tooth position (molar or premolar), and patient dental history variables. A term representing the individual practitioner will be included in the model as a random effect. Study arm, region and terms representing each of the clinical characteristics of the lesions will be included as fixed effects. Initial analyses will be conducted considering each of the clinical characteristic variables singly, along with region and the random effect term, to determine whether there is a significant "univariate" association between the potential predictor and the outcome. Following this series of analyses, a multi-variable approach will be used to evaluate the joint association between the clinical characteristics and the outcome. This analysis will include the practitioner term as a random effect, region, and all of the clinical characteristics that were associated with dentin involvement, at p < 0.10, in the "univariate" analyses. The liberal significance level, using p < 0.10, will be used in order to allow for the possibility that some variables may become more significant in the multivariable approach than in the "univariate" analyses. Further analysis may be conducted, in which non-significant predictors are removed from the multivariable model in order to obtain a more concise prediction model.

Additional descriptive analyses will be conducted to evaluate possible association of practitioner and patient characteristics with outcome measures or other study variables. Depending on the specific structures of these auxiliary analyses, appropriate analysis models may include hierarchical methods, or single-level approaches such as contingency table analysis using the Chi-square statistic or ordinary analysis of variance or logistic regression analyses.

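### Appendix E's one-at-a-time p < 0.10 screen can drop a lesion cue that eligibility itself selects on, although the joint model would detect it

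*Protocol*

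**What the plan says.** Section 5.1 lists tooth criteria that must all be met. One is "Caries into dentin is suspected due to roughness, surface opacities, or staining". A lesion showing none of these signs cannot enter.

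Appendix E names the candidate predictors as "luster, color, roughness on examination with explorer, tooth position (molar or premolar), and patient dental history variables". The analysis set "will include all SOCLs that were treated operatively by the study practitioners". The procedure has two steps. First, "Initial analyses will be conducted considering each of the clinical characteristic variables singly, along with region and the random effect term". Second, the multivariable model takes in "all of the clinical characteristics that were associated with dentin involvement, at p < 0.10", plus region and the practitioner term. Appendix E justifies the liberal threshold by noting that variables can gain significance once modelled jointly. It does not mention selection through eligibility and gives a screened-out variable no way back.

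Earlier in the same paragraph, Appendix E says that study arm, region and a term for every clinical characteristic are fixed effects in the model. That sits uneasily with the later screen but does not remove it. Section 11.1 sets a separate null hypothesis of no association for each characteristic and a joint null for the set included in the model.

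**The concern.** Eligibility and the predictor list draw on overlapping signs. Roughness appears in both by name, staining corresponds to color, and surface opacities relate loosely to luster. Because the cell with no cue is empty by design, the reference group in each single-cue test is enriched for the other cues. If those cues also raise the risk of dentin involvement, as their use as grounds for suspicion suggests, the reference group's risk goes up and the single-cue odds ratio moves toward 1.

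A model holding the cues together compares like with like and is far less exposed. Appendix E nevertheless lets the single-cue result decide which cues reach that model. Identifying the characteristics that best predict dentin caries is a stated secondary objective, and the loss here is a true predictor that never reaches the joint fit.

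**Working it through.** **The plan's own figures.** The protocol states no figure for the screen. The nearest is the Section 11.2 power row for dentin caries of 50% versus 65% among 300 and 210 opened lesions. Dividing each group by 1 + 19 × ICC, with two-sided alpha 0.025, gives 87/80/74/67/62/57% for ICC 0 to 0.05. The stated row is 87/80/73/67/61/56%, so the section's sample sizes and clustering logic reproduce.

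**Inputs from the protocol.**
- Opened lesions in the intervention phase: 300 + 210 + 210 = 720, or 720/90 = 8 per practitioner.
- ICC 0.05, the top of the stated range: design effect 1 + (8 − 1) × 0.05 = 1.35; effective n = 720/1.35 = 533.
- Dentin rate among opened lesions 50% (the no-device assumption, applied overall).
- Screen at p < 0.10, taken as two-sided.

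**Assumed, because the protocol gives none.** Three binary cues, independent before eligibility, with equal prevalence; conditional odds ratios of 2 for the cue under test and 3 for each of the others.

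**Worked case, prevalence 40%.**
1. The excluded no-cue cell is 0.6³ = 0.216, so 0.784 is retained. The tested cue's prevalence becomes 0.4/0.784 = 0.51.
2. With the tested cue absent, a given other cue is present in 0.4/(1 − 0.36) = 62.5%; with it present, in 40%.
3. An intercept of −1.462 gives 50% dentin caries overall.
   - Cue present: 0, 1 or 2 other cues with weights 0.36, 0.48, 0.16 and risks 0.317, 0.582, 0.807. Mean risk 0.522.
   - Cue absent: 1 or 2 other cues with weights 0.75, 0.25 and risks 0.410, 0.676. Mean risk 0.477.
4. Single-cue odds ratio = (0.522/0.478)/(0.477/0.523) = 1.20. Without the eligibility restriction it is 1.84.
5. The standard error of the log odds ratio at n = 533 is 0.173, so z = 0.183/0.173 = 1.06. Chance of passing = Φ(1.06 − 1.645) + Φ(−1.06 − 1.645) ≈ 28%. Without the restriction it is 96%.
6. In the joint model the standard error is 0.198, so z = 0.693/0.198 = 3.50 and power at p < 0.05 = Φ(3.50 − 1.96) ≈ 94%.

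**Across prevalences (odds ratios 2, 3, 3).**

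| Prevalence of each cue | Single-cue OR, no restriction | Single-cue OR, with eligibility | Passes screen | Joint power, p < 0.05 |
|---|---|---|---|---|
| 30% | 1.86 | 1.05 | 11% | 90% |
| 40% | 1.84 | 1.20 | 28% | 94% |
| 50% | 1.84 | 1.36 | 54% | 95% |
| 60% | 1.84 | 1.51 | 74% | 94% |
| 70% | 1.86 | 1.67 | 83% | 92% |

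The joint figures use a stricter threshold than the screen, so the gap is not an effect of the threshold.

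**Simulation check.** GEE with exchangeable correlation, 90 practitioners and about 8 lesions each, gave pass rates of 30% at 40% prevalence and 14% at 30%, with joint detection of 98% and 95%.

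**Other settings.**
- All three odds ratios 2: passes in 68% at 40% prevalence and 88% at 60%.
- Positively correlated cues (latent r 0.3, odds ratios 2, 3, 3, 40%): passes in 72%.
- An odds ratio 3 cue beside cues of 2 and 3, at 40%: passes in 98%.
- Other cues with no effect: the odds ratio stays at 2.00, with no loss.
- Other cues protective (odds ratio 0.5 each, 30%): the odds ratio rises from 1.94 to 2.88.
- Both study phases pooled, with 50% of pre-intervention lesions opened: 1,800 × 0.5 + 720 = 1,620 lesions, 18 per practitioner, design effect 1 + 17 × 0.05 = 1.85. The odds ratio 2 cue beside two of 3 passes in 12% at 30% prevalence and 39% at 40%, against 99% joint power in both.

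**The case against.** **The mapping is partly assumed.** Only roughness matches by name, and opacities and staining might both be coded as levels of color. This stands. The three-binary-cue model illustrates the mechanism and does not describe the trial's data.

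**The inputs decide the size.** With common cues, a dominant cue or positively correlated cues, the loss is modest. A reader might infer that the screen is always biased against these cues. The documents do not support that: the direction depends on the other cues also raising risk.

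**The joint model is not free of selection either.** Eligibility includes the practitioner's suspicion, and the analysis set is limited to lesions the dentist chose to open, with a device in two arms. A reader might infer that joint coefficients are untouched. They are less affected, and the joint-power column assumes no further distortion.

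**Section 11.1 is not wrong.** One might infer that its per-characteristic tests rest on an invalid association. Section 2.1 defines these lesions as showing some of the signs, so cue-free teeth lie outside the target population. The marginal association among operated lesions is therefore a legitimate quantity, and "For each of the clinical characteristics that is considered, the null hypothesis is that there is no association with extension into dentin" can be tested on it. Preferring the conditional coefficient there is a choice of estimand.

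**Appendix E anticipates suppression through p < 0.10.** It recognises the risk, but the allowance does not protect a cue whose single-cue odds ratio is near 1, because the pass rate then falls to about 10%. The joint test in Section 11.1 covers only the characteristics that reached the model, so it cannot restore one already dropped.

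**Conclusion.** The point holds as a weakness in a variable-selection rule that Appendix E states explicitly. Eligibility selects on cues that overlap the candidate predictors, and the one-at-a-time screen can then exclude a cue that the joint model would detect. Under the stated assumptions, an odds ratio 2 cue beside two odds ratio 3 cues passes in about 11% to 83% of trials as prevalence runs from 30% to 70%, against 90–95% joint power. These figures are conditional on independent binary cues, 720 opened lesions, ICC 0.05 and effects that the protocol does not supply. The matter is confined to a secondary objective. It merits a wording change because the rule is explicit and the remedy needs no new data.

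**What to change.** In Appendix E, state that color, luster and roughness enter the multivariable dentin model together whatever their univariate p-values. This agrees with that appendix's own statement that a term for every clinical characteristic is a fixed effect, and it settles the tension with the screening sentence. Label the single-cue results as marginal, descriptive associations among operatively treated lesions. The p < 0.10 screen may remain for the other candidates, but any later pruning of non-significant terms should not remove these three.

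Section 11.1 needs no change. Tooth position need not be forced in, because it is not one of the signs that eligibility selects on. The cost is a few extra model terms, which about 360 dentin events (50% of 720) can carry.

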5.2 Strategies for Recruitment and Retention

Practitioner: Practitioners will be recruited based on the inclusion criteria stated above. They will submit their logs and example CRFs to the RCs (according to regionally approved secure data handling procedures) on a weekly basis to ensure their compliance with the study requirements.

We will need 90 practitioners to participate, or approximately 15 per region for the full study. Each region will recruit two additional practitioners who will serve as back-up participants for the study if a practitioner drops out prior to randomization. These back-up practitioners will complete in-office training, the pre-study vignette, and the pre intervention phase of the study. An additional six practitioners or approximately one per region will be recruited for the pilot phase of the study. Thus the overall number of practitioners in the study will be 108.

Practitioners who meet eligibility criteria will be surveyed for interest in participating in the study. We will rely on the RCs from the six RASs to help recruit practitioners into the study. RCs are 'the face of the nation's network', and many have strong, positive relationships with network members. Practitioners will be compensated for the time required to do the research, receiving \$50 for the pre-study vignette, \$25 for completing the patient assessment CRFs for each patient s/he enrolls, \$50 for the post-study vignette, and \$25 for the post-study questionnaire (both device and no device arms).

Patient: This study requires no post-treatment follow-up, and hence retention of patients is not needed. Patients will be recruited by the practitioner when they are seen in the office and are diagnosed with a SOCL. Designated office personnel will introduce the study to patients who meet inclusion criteria when they are seen for a dental appointment. For patients who express interest in participating in the study, a designated individual will execute regionally approved consent procedures with the patient. It is presumed that these patient recruitment tasks will be consolidated to one or two office personnel. However, each office should have the latitude to designate tasks that will work best within the normal operating procedures for their practice. Enrolled subjects will not receive any compensation for their participation in the study.

5.3 Subject Withdrawal

Practitioners: As part of the study Quality Assurance (QA) program practitioners will be asked to submit their logs and examples of completed CRFs on a weekly basis. Practitioners will be monitored regularly to ensure they adhere to the protocol. Practitioners may withdraw from the study at any time or be withdrawn from the study during the pre-intervention stage if they are unable to enroll at least five patients who present with a SOCL during the first two weeks.

Patients: Subjects may withdraw voluntarily from the study.

5.3.1 Reasons for Withdrawal

Practitioner: Practitioners may choose to withdraw from the study if they are unable or unwilling to adhere to the protocol.

Patient: Subjects are free to withdraw from participation in the study at any time upon request. Since most patients will be seen for one visit, it will be rare for a patient to withdraw from the study.

An investigator may terminate a study subject's participation in the study if:

- Any clinical adverse event (AE) or situation occurs such that continued participation in the study would not be in the best interest of the subject.
- The subject meets an exclusion criterion (either newly developed or not previously recognized) that precludes further study participation.

5.3.2 Handling of Subject Withdrawals

Practitioner: If a practitioner withdraws from the study prior to randomization, he/she will be replaced by another practitioner. If the practitioner withdraws from the study after randomization, he/she will not be replaced.

Patient: We expect the withdrawals will be extremely infrequent. If a patient withdraws due to an unanticipated event, we will follow-up to determine if it constitutes an unanticipated problem.

5.4 Premature Termination or Suspension of Study

This study may be suspended or prematurely terminated if there is sufficient reasonable cause. Written notification, documenting the reason for study suspension or termination, will be provided by the suspending or terminating party. If the study is prematurely terminated or suspended, the principal investigator will promptly inform the IRB and will provide the reason(s) for suspension or termination.

Circumstances that may warrant termination include, but are not limited to:

- Determination of unexpected, significant, or unacceptable risk to subjects;
- Insufficient adherence to protocol requirements;
- Data that are not sufficiently complete and/or evaluable; and
- Determination of futility.

6 STUDY SCHEDULE

Those National Dental PBRN dentist practitioners who opt to participate will be sent information and instructions pertaining to the study. These instructions will provide information for the dentist(s) and staff who will help to execute the study. A detailed Practice Training Binder will be provided to each practice in written form prior to initiation of the study in the practice. The Practice Training Manual will carefully describe the subject selection procedures, methods for approaching subjects and obtaining informed consent (according to regional approvals), methods for data collection, and other study procedures. A summary flow chart will be sent to the practices with a description the study visit and an overview flow chart of the study. This will provide a simple, single page reference for office personnel involved in the study. In addition, in-person meetings (or teleconferences) with office staff will be held to provide further instruction in completing CRFs. The RC will also meet (or have an individual telephone call) with the participating practitioners prior to initiating the study to make sure that they and their office staff understand the study procedures.

The study will proceed in stages: 1) each region will enroll practitioners into the study who have completed IRB-mandated training; 2) practice personnel receive necessary IRB training and mail or in-person visits to have them sign practitioner informed consent forms (if required by that region's IRB), UAB Master Service Agreement, and similar documents; 3) RCs will ensure practices are trained in the appropriate study procedures (see below); 4) practices enroll subjects into the study. The CC along with the RAS and RCs will coordinate the launch of the study. Once the RC has trained an office in the practice procedures, that practice should begin recruiting subjects into the study immediately, or as soon as possible.

An overview of study procedures to be completed at each study visit can be found in Appendix A.

6.1 Practitioner:

